**TITLE:**

Healthy Introduction of Complementary Foods: An Obesity Prevention Program

**1. PURPOSE of the research project AND GENERAL INFORMATION:**

a. **PURPOSE**

The purpose of this research study is to pilot test a prevention program to promote healthy introduction of solid foods and healthy weight gain among infants. Introduction of complementary foods (i.e., foods besides formula or breast milk) represents a major dietary milestone for infants, but there are currently no empirically-derived guidelines for how parents should introduce solid foods to their infants. The current study will test the feasibility of a 3-session intervention encouraging healthy introduction of complementary foods and use of a responsive feeding approach. Feasibility of the intervention and the impact of the Healthy Start to Feeding (HSF) intervention on obesity risk factors and growth will be explored. This will be achieved through exploration of the following aims and hypotheses:

**Aim 1: Determine feasibility of the intervention and family satisfaction with the treatment.**

H1: Families assigned to the intervention condition will attend  $\geq 67\%$  of treatment sessions.

H2: Families receiving the intervention will rate the program as helpful and consistent with the families' needs and priorities.

**Aim 2: Test the impact of the HSF intervention on growth trajectories, appetite regulation, and diet at post-treatment.**

H1: Infants receiving the intervention will experience lower incidence of high weight-for-length ( $\geq 85^{\text{th}}$  percentile) compared to infants in the control condition.

H2: Infants in the treatment condition will show greater satiety responsiveness and lower food responsiveness as assessed through a well-validated parent-report measure (*Baby Eating Behavior Questionnaire* (Llewellyn, van Jaarsveld, Johnson, Carnell, & Wardle, 2010)).

H3: Infants in the treatment condition will consume a greater variety of fruits and vegetables than infants in the control condition as assessed through a food frequency questionnaire completed by parents.

b. **BACKGROUND**

1) Prior research

Pediatric obesity occurs at epidemic rates (Ogden, Carroll, Kit, & Flegal, 2014) with significant health, financial, and psychosocial consequences (Weiss & Kaufman, 2008; Williams, Wake, Hesketh, Maher, & Waters, 2005; Griffiths, Parsons, & Hill, 2010; Freedman, 2007). While many treatments for pediatric obesity exist, obesity remains intractable for many children, and most children participating in treatments do not exhibit clinically meaningful reductions in Body Mass Index. Therefore, prevention of obesity is critical, including prevention efforts within the first year of life. Children with severe obesity begin to deviate in their growth trajectories at as early as 4 months of age (Smego et al., 2017). Infants with high weight-for-length have up to a 9 times greater risk of obesity later throughout the lifespan, even until 60-70 years of age (Baird et al., 2005; Eriksson, Forsen, Osmond, & Barker, 2003). However, effective prevention programs targeting children  $< 2$  years are limited (Blake-Lamb et al., 2016).

Interventions promoting use of responsive feeding (RF) practices have shown promise in reducing obesity-risk among young children (Savage et al., 2016). RF is characterized by parental attunement to child hunger and feeding cues and use of these cues by parents to structure and make decisions about feeding situations. Responsive parents offer foods when indicated by child hunger cues and allow children's own satiety cues to determine when a feeding is complete, rather than pressuring children to eat the amount of food pre-determined by the parent. Responsive parenting is hypothesized to reduce obesity-risk by allowing children to develop awareness and responsiveness to their own satiety cues. However, the concept of RF has rarely been applied to the key dietary transition of introduction to complementary foods. Research on the introduction of complementary foods and infant weight gain has predominantly focused on the timing of introduction with little research exploring the potential impact of weaning style or the manner in which complementary foods are introduced, including whether a RF approach to introduction of complementary foods results in reduced obesity risk. There are currently no empirically-derived recommendations for parents on *how* to introduce complementary foods to infants.

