#### **4. DATA ANALYSIS:**

Aim 1 (Determine the feasibility of the *HSF* intervention and family satisfaction with the treatment) will be explored using descriptive analyses. We will calculate the average number of treatment sessions attended and the percentage of participants attending 2 (67%) and 3 (100%) of the sessions. Additionally, we will calculate the percentage of caregivers who either "somewhat agree" or "strongly agree" that the intervention is appropriate, timely, helpful, and satisfactory as assessed by the Treatment Satisfaction Survey. Qualitative comments on the Treatment Satisfaction Survey will also be reviewed to identify themes regarding additional information to include in the intervention, what information was most helpful, what caregivers would like to see changed about the intervention, and what they would like to see stay the same.

Aim 2 (Examine the impact of the *HSF* intervention on growth trajectories, appetite regulation, and diet at post-treatment) will be explored through group comparisons between the control and treatment groups on weight-for-length scores, subscale scores of the *BEBQ*, and number of fruits and vegetables consumed in the last week as assessed on a food frequency questionnaire. Prior to between group comparisons, potential differences between the control and treatment group on key sociodemographic and baseline variables (e.g., gender, baseline weight-for-length, household income, caregiver education level) will be explored to confirm the

effectiveness of randomization to treatment condition. A series of Analysis of Variance (ANOVA) will be computed to examine whether the control and treatment groups differ on outcome variables. If missing data are present, we will also consider an alternative analyses using a repeated measures model with maximum likelihood estimation to examine group differences on outcome variables, which will allow inclusion of all participants despite missing data.

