College of Arts and Sciences
Department of Psychology
University of Cincinnati
Cincinnati, OH, 45221

Official Title: Healthy Start to Feeding Pilot Trial

Brief Title: Healthy Start to Feeding Intervention

NCT Number: NCT03597061

Document Date: 7/9/2018

Date Uploaded: 6/24/21

Document: Statistical Analysis Plan

Statistical Analysis Plan

Primary Aim (Examine the impact of the HSF intervention on growth trajectories, appetite regulation, and diet at post-treatment) was explored through group comparisons between the control and treatment groups on weight-for-length scores, subscale scores of the BEBQ, and number of fruits and vegetables consumed in the last week as assessed on a food frequency questionnaire. Prior to between group comparisons, potential differences between the control and treatment group on key sociodemographic and baseline variables (e.g., gender, baseline weight-for-length, household income, caregiver education level) were explored to confirm the effectiveness of randomization to treatment condition. A series of Analysis of Variance (ANOVA) were computed to examine whether the control and treatment groups differed on outcome variables.

Secondary Aim (Determine the feasibility of the HSF intervention and family satisfaction with the treatment) was explored using descriptive analyses. We calculated the average number of treatment sessions attended and the percentage of participants that attended 2 (67%) and 3 (100%) of the sessions. Additionally, we calculated the percentage of caregivers who either “somewhat agree” or “strongly agree” that the intervention was appropriate, timely, helpful, and satisfactory as assessed by the Treatment Satisfaction Survey. Qualitative comments on the Treatment Satisfaction Survey were also reviewed to identify themes regarding additional information to include in the intervention, what information was most helpful, what caregivers would like to see changed about the intervention, and what they would like to see stay the same.

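### Aim 2 H1 is about the proportion of infants at or above the 85th weight-for-length percentile, but the planned analyses compare mean scores and give no estimate of that proportion

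*Protocol*

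**What the plan says.** Protocol section 1.a, Aim 2, gives the growth hypothesis as "H1: Infants receiving the intervention will experience lower incidence of high weight-for-length" and sets the threshold at the 85th percentile or above, compared with control.

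Protocol section 4 says Aim 2 "will be explored through group comparisons between the control and treatment groups on weight-for-length scores", together with appetite subscales and fruit and vegetable counts. The method is: "A series of Analysis of Variance (ANOVA) will be computed to examine whether the control and treatment groups differ on outcome variables". If data are missing, "we will also consider an alternative analyses using a repeated measures model with maximum likelihood estimation to examine group differences on outcome variables".

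The SAP places these outcomes under its Primary Aim. It lists "group comparisons between the control and treatment groups on weight-for-length scores, subscale scores of the BEBQ, and number of fruits and vegetables consumed" and then says: "A series of Analysis of Variance (ANOVA) were computed to examine whether the control and treatment groups differed on outcome variables". It does not mention the repeated measures alternative.

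Three other places bear on the point:

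- Protocol 3.c.3(c) obtains WHO weight-for-length percentiles from measurements at the initial and final visits.
- Protocol 2.a.2 admits infants with normal or elevated weight-for-length, provided they are at or above the 10th percentile.
- Protocol 2.a.1 sets 20 infants per arm on grounds of feasibility.

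**The concern.** H1 concerns how many infants lie above a cut-off. The planned analyses concern where the arm averages lie. These are different quantities, and one does not determine the other. If the plan is followed to the letter, the report will contain a mean difference, and a reader will not learn whether high weight-for-length was less frequent in the treated arm.

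There is a second, smaller gap. Because infants already above the 85th percentile can enrol, a 9-month case may be new or may have been present at entry. The Aim 2 heading fixes the time point as post-treatment, but does not say whether incidence means all cases at that visit or only new ones. Randomisation keeps the arm comparison fair either way, but the report has to say which quantity it gives.

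**Working it through.** **1. Hypothesis against analysis.** The plan states no alpha, power, effect size or event rate, so it has no figure to reproduce. The check is a comparison of text.

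| | Hypothesis | Planned analysis |
|---|---|---|
| Aim 1 H1 | "H1: Families assigned to the intervention condition will attend" at least 67% of sessions | "the percentage of participants attending 2 (67%) and 3 (100%) of the sessions" |
| Aim 2 H1 | Lower incidence at or above the 85th percentile | Weight-for-length scores, by ANOVA or possibly a repeated measures model |

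Section 4 carries the Aim 1 threshold into the analysis but not the Aim 2 threshold. Neither the protocol nor the SAP names a proportion, risk difference, risk ratio, odds ratio or any method for a binary outcome in Aim 2.

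**2. Same mean difference, different tail.** Assume normal z-scores. The 85th percentile is z = 1.036, and the share above it is 1 − Φ((1.036 − m)/s). For controls with m = 0 and s = 1 this is 15.0%. For a treated mean of −0.3 the numerator is 1.336:

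- s = 1.0: 1.336/1.0 = 1.336, giving 9.1%
- s = 0.8: 1.336/0.8 = 1.670, giving 4.7%
- s = 1.35: 1.336/1.35 = 0.990, giving 16.1%

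**3. The same point with the entry criterion built in.** Assume the 3-month z-score b follows the reference above the 10th percentile, and the 9-month score is y = r·b + √(1 − r²)·e with e standard normal and r = 0.4 or 0.7 (4,000,000 simulated infants). The control share at or above the 85th percentile is 0.163 (r = 0.4) or 0.167 (r = 0.7). Each treated scenario below has a mean difference of −0.3; a shift of −0.6 in half the infants gives 0.5 × (−0.6) = −0.3.

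| Who shifts | r = 0.4 | r = 0.7 |
|---|---|---|
| Everyone, by −0.3 | 0.099 | 0.101 |
| Lower half only, by −0.6 | 0.163 | 0.167 |
| Upper half only, by −0.6 | 0.056 | 0.056 |

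**4. New and pre-existing cases, same model.** With entry cut at the 10th percentile, 15/90 of infants are at or above the 85th percentile at entry: 15/90 × 20 = 3.3 per arm. Among 20 controls at 9 months:

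- r = 0.4: 2.17 new and 1.09 pre-existing, so 1.09/3.26 = 33% were cases at entry
- r = 0.7: 1.59 new and 1.74 pre-existing, so 1.74/3.33 = 52% were cases at entry

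**5. Precision of the missing estimate.** Exact unconditional 95% intervals for the risk difference (inverted two-sided score test), 20 per arm:

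- 2/20 against 4/20: −10 points, interval −34 to +14, width 48
- 3/20 against 6/20: −15 points, interval −41 to +12, width 53

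Two-sided Fisher power for a halved rate at an assumed alpha of 0.05 is 4%, 7%, 12% and 19% for assumed control rates of 15%, 20%, 30% and 40%.

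**6. Baseline adjustment of the continuous outcome.** In 100,000 simulated trials from the same model, adjusting the 9-month z-score for the 3-month z-score reduces the standard error of the arm difference from 0.308 to 0.293 SD (r = 0.4, 5% lower) or from 0.293 to 0.229 SD (r = 0.7, 22% lower).

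**The case against.** The strongest reply has four parts.

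- **Scores is undefined and the ANOVA is on generic outcome variables.** An ANOVA on a 0/1 indicator would compare proportions. That is true, but no section derives such an indicator, so the estimate is still unplanned.
- **This is an exploratory pilot, and a continuous comparison is sensible at 40 infants.** This stands as to weight. Sections 1.a and 4 describe the effects as explored, and the SAP's Primary Aim covers growth, appetite and diet together. It does not remove the mismatch: an exploratory hypothesis still needs an estimate of what it names.
- **The added estimate would tell a reader little.** This largely stands. At a control rate of 16-17% the standard error of the difference is about 10 to 12 points, so the scenarios in step 3 could not be reliably separated. The 4/20 and 6/20 control counts in step 5 also exceed the model's own 3.3/20, where Fisher power for a halved rate is about 5%. The half-sample shifts are deliberate extremes; they show what is possible, not what is likely. All of this argues for an interval and against a test.
- **Baseline adjustment is a separate matter.** Fair: it concerns efficiency, not the H1 mismatch, and the gain may be only 5%. It costs nothing, since the baseline value is already collected, but it adds no weight to the main point.

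**Conclusion.** The concern holds. H1 names a threshold outcome, and neither the protocol nor the SAP plans an estimate of it. This follows from the text alone and needs no modelling assumption.

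The sizes are illustrative. They rest on reference-like z-scores above the 10th percentile at entry and an assumed 3-to-9-month coefficient of 0.4 to 0.7; the documents give neither. On that basis, one mean difference of −0.3 SD is compatible with anything from no reduction (16-17%) to a fall to 6%, and a third to a half of 9-month control cases would have been cases at entry.

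This is a specification gap that should be fixed. It does not bias the randomised comparison.

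**What to change.** **Align H1 with its analysis, by one of two routes.**

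- *Option A.* In Aim 2, define the H1 outcome as the proportion at or above the 85th WHO weight-for-length percentile at the 9-month visit. Add to protocol section 4 and the SAP: The number and proportion of such infants will be reported by arm, with the between-arm difference and an exact unconditional 95% interval, as an estimate without a significance claim. New cases among infants below the 85th percentile at entry will be listed by arm as counts.
- *Option B.* Reword H1 as a lower mean weight-for-length z-score at 9 months.

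The SAP is written in the past tense. If results have been seen, Option A is easier to defend, because Option B would change a hypothesis afterwards.

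**Under either option,** state that the continuous outcome is the 9-month weight-for-length z-score (the plan leaves the kind of score open) and adjust it for the 3-month z-score. Under Option A, label this a comparison of means and not the test of H1.

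**Cost.** Wording in Aim 2, section 4 and the SAP, plus one small table; no new data. The interval for the proportion will be wide and will probably include zero, and the gain from adjustment is small if r is near 0.4. Date the additions and label them as clarifications.

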**2. PARTICIPANTS:**

a. RECRUITMENT

Participants will be recruited at 2-3 months of age through Pediatric Associates, PSC, a pediatrician practice that has 3 locations in northern Kentucky. If adequate enrollment cannot be achieved through Pediatric Associates, an amendment will be submitted to expand recruitment

to include daycares, Sona system (i.e., student participants can enroll if they have a child meeting study inclusion criteria), and internet and social media sites for our research lab (i.e., The Healthy Kids Lab).

1) Number of participants

The study will enroll 40 total participants. Twenty participants will be randomized to receive the study treatment and 20 participants will be randomized to the control group.

(b) Rationale

This number of participants was determined based on the number of participants feasible to enroll as part of a pilot study while still generating enough data regarding treatment feasibility.

2) Inclusion and exclusion criteria

Participants will be infants aged 3-9 months and their families ( $n = 40$ ). Infants with both normal and elevated weight-for-length will be enrolled. Inclusion criteria include 1) infant has not previously been introduced to complementary foods (i.e., any food besides formula or breastmilk), 2) infant does not have a known developmental delay, 3) infant does not have impaired fine or gross motor skills (which would impact ability for self-feeding), 4) infant does not have a condition currently impacting their feeding and eating, 5) infant born at  $\geq 38$  weeks gestation, 6) infant current weight-for-length  $\geq 10^{\text{th}}$  percentile (Infants with suboptimal growth will be excluded due to potential safety implications of modifying eating and feeding styles of infants with growth difficulties), and 7) parent is a fluent English speaker (because this is the language the intervention will be delivered in).

3) Vulnerable participants

(a) Vulnerability

All study participants will be children less than 1 year old.

(b) Rationale

The objective of the current study is to test an intervention for healthy infant feeding. Therefore, all participants are required to be infants.

(c) Confirmation

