Study participants will be assigned to either the control or treatment condition at their first study visit following completion of informed consent and baseline measures. A computer-generated random number list will be used to determine condition assignment for each participant. Participants will be notified immediately at the study visit of their study condition.

(b) Activities and duration

The first study appointment will occur when the infant is 3 months of age (defined as 3 months 0 days – 3 months 30 days) at the Schubert Research Clinic (SRC) at CCHMC. The infant and at least one parent will attend the appointment. The appointment will begin with completion of the informed consent process with the study PI or trained research assistant. Next, participants will

complete study measures, including infant anthropometrics and parent-report measures of demographics, parental feeding practices and beliefs, and infant appetite. Families will also receive information about how to intervene if their child experiences a choking incident while introducing complementary foods. Following completion of study measures, families will be randomized to either the control or treatment condition using a computer-generated random number list. Participants will receive \$50 for completion of this visit. Participants in the intervention condition will be instructed to not introduce their child to complementary foods prior to their first Treatment Session at 4 months of age. All families will receive safety information regarding monitoring infant growth and choking.

Participants assigned to the treatment condition will attend 3 intervention sessions at the Healthy Kids Lab, located in the Edwards Center on UC campus. The sessions will be scheduled with individual families when the child is 4 months (+/- 30 days), 6 months (+/- 30 days), and 9 months (+/- 30 days) of age. An attendance log of whether participants attend treatment will be kept.

All participants will also complete a final study visit at the SRC at CCHMC when the child is 9 months (+/- 30 days) of age. They will complete a final study visit to complete post-treatment period measurements, which will include infant anthropometrics and parent-report of infant appetite, infant diet, and parental feeding practices and beliefs. Families receiving the intervention will also complete a measure of treatment satisfaction. Participants will receive \$50 for completion of this visit.

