**(c) Data collection tools**

Infant Anthropometrics. Anthropometrics will be measured for pre-post analyses at both the initial and final study visit by Bionutrition Core staff at the SRC. Infant length will be measured in triplicate to the nearest 0.1 centimeter using an infant length board (O'Leary, Ellard Instrumentation, LTD). Weight will be measured in triplicate to the nearest 100 grams with the infant in a dry diaper using a Scale Tronix 4802 digital infant/pediatric scale. The average of the three measurements will be used to calculate weight for recumbent length. Percentiles for each infant's weight for recumbent length will be obtained using sex and age specific World Health Organization (WHO) growth charts. Information will be recorded on the "Anthropometrics Form".

For families in the intervention condition, infants will also have length and weight measured at each treatment session to monitor safety of growth. Measurements will be taken by study interventionists using a SECA infant length board (SECA 416) and SECA infant digital scale (SECA 374).

Infant and Family Demographics. Demographics information will be collected at the initial study visit using a form created for use in this study.

Treatment Satisfaction. Caregivers in the treatment condition will complete a survey to provide quantitative and qualitative feedback on the intervention after the final treatment session. The questionnaire includes Likert scale ratings of the appropriateness, helpfulness, and timeliness of session content as well as open-ended questions for the parent to provide qualitative feedback on ways to improve the intervention (e.g., additional content to cover).

Infant Appetite. Parents will complete a survey entitled the *Baby Eating Behaviour Questionnaire* (Llewellyn et al., 2010) at both the initial study visit and final study visit or final treatment visit to assess current infant appetite. Parents respond to 17 items on a 5-point scale. Scores for "Enjoyment of Food", "Food Responsiveness", "Slowness in Eating", and "Satiety Responsiveness" are calculated.

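### Aim 2 H1 predicts lower incidence of weight-for-length at or above the 85th percentile, but infants already at that level can be enrolled, so the all-infant comparison at 9 months measures prevalence

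*Protocol*

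**What the plan says.** Protocol section 1.a, Aim 2 H1, predicts that "Infants receiving the intervention will experience lower incidence of high weight-for-length", defined as the 85th percentile or above, relative to control.

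Protocol section 2.a.2 says "Infants with both normal and elevated weight-for-length will be enrolled". The only weight-for-length limit is a floor at the 10th percentile, explained by the statement that "Infants with suboptimal growth will be excluded due to potential safety implications of modifying eating and feeding styles of infants with growth difficulties". There is no ceiling.

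On numbers, section 2.a.1 says "Twenty participants will be randomized to receive the study treatment and 20 participants will be randomized to the control group". The rationale is feasibility: "This number of participants was determined based on the number of participants feasible to enroll as part of a pilot study".

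On timing, section 3.c.3(b) says "Following completion of study measures, families will be randomized to either the control or treatment condition using a computer-generated random number list", so the 3-month weight and length are recorded before allocation. Section 3.c.3(c) adds that "Anthropometrics will be measured for pre-post analyses at both the initial and final study visit".

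Protocol section 4 and the SAP's Primary Aim paragraph compare the arms by ANOVA on weight-for-length scores. In both, baseline weight-for-length appears only in a check that randomisation worked. Section 4 also says a repeated-measures model will be considered if data are missing; the SAP does not mention it. Neither document describes stratified allocation, a new-onset event, or an analysis set restricted to infants below the cut-off at entry.

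**The concern.** Incidence means new cases among those free of the condition at the start. An infant at or above the 85th percentile at 3 months already has the H1 outcome and cannot become a new case. A 9-month count over all infants therefore adds two groups together: infants who crossed the cut-off after randomisation and infants who were above it throughout.

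For a prevention programme these are different questions. If the all-infant figure were reported as incidence, a lower figure in the intervention arm could reflect fewer new cases, more resolution among infants already high, or a chance difference at entry. The reader could not tell which. With 20 per arm the last possibility is not negligible, and the planned ANOVA does not correct for it.

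A separate gap is that an ANOVA on weight-for-length scores does not test a binary hypothesis. Adding a comparison of proportions would close that gap but would still not yield incidence.

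**Working it through.** The documents give no event rate, power or effect size for H1, so there is no planned figure to reproduce. The allocation is consistent (20 + 20 = 40).

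**Inputs from the protocol:** 40 infants, 20 per arm; entry floor at the 10th percentile; outcome cut-off at the 85th; WHO growth charts as the reference.

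**Assumptions, not in the documents:** enrolled infants follow the reference distribution above the floor; z-scores at 3 and 9 months are bivariate normal with correlation ρ; there is no treatment effect; all 40 infants are measured at 9 months.

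**Step 1. Already high at entry.** 0.15 / 0.90 = 16.7%, and 40 × 0.167 = 6.7 infants (3.3 per arm). That leaves 40 − 6.7 = 33.3 at risk of new onset. The chance of enrolling at least one infant already high is 1 − (5/6)^40 = 0.999.

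**Step 2. Make-up of the 9-month cases.** Let Z3 and Z9 be the z-scores, and c10 and c85 the cut-offs.
- Share already high = P(Z3 ≥ c85, Z9 ≥ c85) / P(Z3 ≥ c10, Z9 ≥ c85)
- New-onset risk = P(c10 ≤ Z3 < c85, Z9 ≥ c85) / 0.75

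| ρ | 9-month prevalence | Share of cases already high at entry | Persistence among those high at entry | New-onset risk below the cut-off | New cases of 40 |
|---|---|---|---|---|---|
| 0 | 15.0% | 17% | 15.0% | 15.0% | 5.0 |
| 0.3 | 16.1% | 29% | 27.7% | 13.8% | 4.6 |
| 0.5 | 16.5% | 39% | 38.5% | 12.1% | 4.0 |
| 0.7 | 16.7% | 52% | 52.1% | 9.6% | 3.2 |
| 0.8 | 16.7% | 61% | 60.9% | 7.8% | 2.6 |

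Check at ρ = 0.5: 33.3 × 0.121 = 4.0 new cases and 6.67 × 0.385 = 2.6 persistent cases. The total is 6.6, and 2.6 / 6.6 = 39%.

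**Step 3. Sensitivity to a heavier sample.** With mean z = +0.3, 24.5% (9.8 of 40) are high at entry, and the share runs from 37% to 67% for ρ from 0.3 to 0.8. With mean z = +0.5, 30.7% (12.3 of 40) are high at entry, and the share runs from 43% to 70%.

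**Step 4. Chance imbalance.** Taking the number already high in each arm as independent Binomial(20, 1/6), P(difference ≥ 3) = 0.28 and P(difference ≥ 2) = 0.52.

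**Step 5. What an imbalance of 3 does.** The expected difference in 9-month cases between arms is 3 × (persistence − new-onset risk).
- ρ = 0.3: 3 × (0.277 − 0.138) = 0.4
- ρ = 0.5: 3 × (0.385 − 0.121) = 0.8
- ρ = 0.8: 3 × (0.609 − 0.078) = 1.6

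The total expected is 6.4 to 6.7 cases over both arms, or about 3.3 per arm.

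**The case against.** The strongest reply is that this is mainly one word. The Aim 2 heading refers to post-treatment, and a natural reading of H1 is the proportion high at 9 months by arm. Elevated infants are enrolled deliberately, and the stated purpose includes healthy weight gain, so resolution among them may be part of the intended benefit. The trial is a pilot sized for feasibility, and the planned balance check would show an imbalance at entry. Much of this stands, and it is why rewording is the main remedy. It does not rescue the word incidence, and a balance check reveals an imbalance without correcting for it. The repeated-measures model would bring in the baseline value, but it is conditional on missing data and defines no new-onset event.

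Three stronger readings are tempting, and the documents do not support them.

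- *The comparison is biased.* A reader might infer this because prevalent cases are included. Measurement precedes randomisation, so infants already high are balanced in expectation.
- *Most 9-month cases would be old ones, or an imbalance is close to an even bet.* The share depends on a correlation that the documents do not give; it is 17% with no tracking. Conditioning on exactly 7 high infants gives a probability of 0.41 for a difference of 3 or more, but an odd total allows only odd differences. The same hypergeometric calculation gives 0.18 for 6 infants and 0.24 for 8. Allowing the count to vary gives 0.28.
- *Any prevention statement must rest on the new-onset subset alone.* That is a choice of estimand the protocol does not make. About 33 infants with roughly 3 to 5 new cases cannot carry it. As an illustration, for a halving from 16.7% to 8.35%, an exact Fisher test (two-sided 5%, assumed) has about 4% power with 17 per arm.

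**Conclusion.** The concern holds as a matter of definition and interpretation. H1 names incidence, the eligibility rules admit infants who may already have the outcome, and no at-risk set or firm baseline adjustment is specified. A comparison of all randomised infants at 9 months is a valid comparison of prevalence, but a claim of lower incidence could not be drawn from it.

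Under the reference-distribution assumption, about 7 of 40 infants are high at entry. They supply 29% to 61% of 9-month cases for ρ from 0.3 to 0.8, and more if the sample is heavier than the reference. The arms differ by 3 or more such infants with probability about 0.28, which would shift the expected case difference by about 0.4 to 1.6. The structural point needs none of these assumptions; its size depends on all of them.

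**What to change.** 1. Reword H1 as a prevalence statement: a smaller proportion of infants randomised to the intervention than to control will be at or above the 85th percentile at the 9-month visit, counting all randomised infants.
2. In protocol section 4 and the SAP, adjust the between-arm weight-for-length comparison for the 3-month value on the same scale, whether or not data are missing. This keeps all 40 infants and deals with chance imbalance directly.
3. Add one table of 9-month status (below, or at or above, the 85th percentile) by 3-month status and arm. It shows new onset, persistence and resolution separately.
4. Use the word incidence only for new onset among infants below the 85th percentile at 3 months, and label it descriptive (about 33 infants and roughly 3 to 5 expected new cases over both arms).

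The cost is a few sentences in each document, one covariate and one cross-tabulation. The measurements are already planned, and eligibility, visits and procedures do not change. The limitation is that the new-onset figure will be imprecise and should not carry a formal conclusion.
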